Project Title: SMART-DAPPER: Leveraging the Depression And Primary-care Partnership for Effectiveness-implementation Research Project (SMART-DAPPER)

Clinicaltrials.gov number: NCT03466346

Title of Document: Statistical Analysis Plan

Date of Document: October 27, 2021

Statistical Analysis Plan

We used an intent-to-treat analysis. We used multivariate normal multiple imputation with 100 imputations to impute missing values of BDI-2 and PCL-5. For both of our primary outcomes (binary) we used generalized estimating equations (GEE) methods to fit a log-link binomial regression model with robust standard errors and a working exchangeable correlation structure to accommodate the repeated measures over time. Because not all participants had both major depression and PTSD at baseline, our analysis models the change in the risk of the outcome from baseline to end of first-line treatment.

Correspondingly, our model included the predictors of time (e.g., baseline and end of treatment), intervention group, the interaction of time, and intervention group. Results are described in terms of relative risks, and, for the interaction, ratios of relative risks with corresponding confidence intervals. The primary test of interest is the time by group interaction.

Secondary outcomes (BDI-2, PCL-5 continuous scores) were numeric, continuous variables. For these analyses we used GEE methods to fit a linear regression model with robust standard errors and a working exchangeable correlation structure. As before, our model included the predictors of time (baseline, end of treatment), intervention group and the interaction of time and intervention group. Results are described in terms of differences in mean values and, for the interaction, differences of differences with corresponding confidence intervals. The primary test of interest is the time by group interaction.

Participants who were not in remission at end of first line treatment were re-randomized to either treatment switch or treatment combination. These randomized comparisons were conducted using Fisher's exact test for MDD or PTSD or an exact Wilcoxon rank-sum test for BDI-2 score or PCL-5 score.

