- Implementation and economic domains include human resources for integrating mental health care within the HIV clinic (implementation officer, peer supervision, clinic staff advisory team), treatment protocol adherence (a random 20% of IPT sessions are externally reviewed for IPT adherence), repeated stakeholder engagement (local and national) and a detailed economics core assessing patient-level benefits, formal and informal productivity gains and overall returns on mental health care investment.

In preliminary analyses of post-treatment data (n=194) in the current study in Kisumu, Kenya, non-specialist delivered IPT achieves MDD remission in 38% and PTSD remission in 52% of participants – greater than treatment as usual and higher than U.S. effectiveness studies (30%) with physician-delivered depression care. In a subsample with HIV viral load data (n=116), we have a nearly significant effect ($p=0.09$) on undetectability of HIV viral load (clinical goal): 82% of those in IPT have undetectable viral loads after their 12-week treatment, versus only 68% of those in usual care, despite the fact that all participants received usual HIV care, throughout.

Expertise and experience in training nurses in East Africa to administer fluoxetine for depression:

Our team has experience with training nurses and clinical officers to integrate with existing healthcare systems and successfully prescribe fluoxetine for depression, including HIV clinics in a neighbouring region of Uganda. In preliminary analyses of [name] and [name]'s INDEPTH study (n=415), 66% (n=272) completed a 9 month course of antidepressant therapy. Only 15% (n=61) had prematurely discontinued treatment —a higher rate of adherence than with SSRIs in High Income Countries (HICs). 78% of completers were in full remission at treatment conclusion and 66% in the intent to treat analysis, which classified those who prematurely discontinued treatment as non-responders. The majority of the treatment gains were achieved early in treatment (weeks 6-12), with a 68.5% average reduction on the Patient Health Question 9 item (PHQ-9) from baseline and little further gain with additional treatment.

Hypothesis and Specific Aims:

Aim 1:

Determine the effectiveness of non-specialist-delivered Interpersonal Psychotherapy (IPT), fluoxetine, or combination for MDD and PTSD.

Hypothesis 1a: Initial randomization to IPT or fluoxetine will have similar efficacy for post-treatment remission.

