Data collection. Data collection will use tablets programmed with Research Electronic Data Capture (REDCap), similar to the electronic data system that we are currently using in Kisumu, Kenya (Online Data Kit [ODK]). REDCap now has an offline feature which does not require internet connectivity for data entry and can be later connected to the internet for upload to secure server.

Effectiveness outcomes

Clinical evaluators. Clinical evaluators will consent and screen study participants, complete baseline measures and then refer participants to (un-blinded) study coordinators for randomization. Blinded to group assignment, clinical evaluators will conduct 1.5 month (IPT treatment mid-point), 3 month (IPT end-of-treatment, fluoxetine-mid-treatment), and follow-up assessments. Candidate clinical evaluators will undergo a two day training during which they will be introduced to the study measures and their proper application. At the conclusion of the training, the candidates will be observed in their administration of the measures, assessing for accuracy and completeness. If successful, they will be evaluated for reliability by conducting a group interview and comparing measure results. Those who demonstrate both accuracy and inter-rater reliability will be invited to join the study. Monetary compensation will be provided for completed measures at the local currency equivalent of 7usd.

Data analysis plan

For *Hypothesis 1a* the analysis is standard intention to treat for 3 month (end of treatment) data. Our basic analysis strategy will be to fit logistic regression models for the outcome of MDD and/or PTSD remission, in this case with the predictor of group assignment (IPT or fluoxetine), demographics and severity of baseline depression and/or PTSD symptoms (BDI and PCL) . *Hypothesis 1b* will be analyzed for the sub-group of participants who are in remission from MDD and/or PTSD at months 1.5 or 1.5 and 3 and will use weighted generalized estimating equations logistic regression to accommodate the repeated measures on this subgroup through month 30.

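### The primary time-by-group interaction measures change in prevalence among everyone randomised, so it mixes remission with new onset, while Hypothesis 1a is about remission

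*SAP*

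**What the plan says.** The SAP announces its analysis set in one line, "We used an intent-to-treat analysis", and names no subset for either disorder. For both binary primary outcomes it will "fit a log-link binomial regression model with robust standard errors and a working exchangeable correlation structure". It gives its reason for modelling two time points, entry and the close of first-line treatment: "Because not all participants had both major depression and PTSD at baseline, our analysis models the change in the risk of the outcome". On the terms in the model it says "our model included the predictors of time (e.g., baseline and end of treatment), intervention group, the interaction of time, and intervention group". The interaction is the primary test, and the SAP promises "for the interaction, ratios of relative risks with corresponding confidence intervals". It states no term for baseline disorder status, no restriction to baseline cases and no separate analysis of new onset.

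The protocol puts the question differently. Hypothesis 1a reads "Initial randomization to IPT or fluoxetine will have similar efficacy for post-treatment remission". The Data analysis plan says the team will "fit logistic regression models for the outcome of MDD and/or PTSD remission", with group, demographics and baseline BDI and PCL severity as predictors. Under Study visits, remission means no longer meeting DSM-V threshold criteria. Entry requires MDD, PTSD or both (Eligibility criteria), and randomisation follows completion of the baseline measures (Randomization and blinding).

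**The concern.** A participant who enters with MDD alone cannot remit from PTSD; that person can only develop it. If such participants stay in the PTSD model, each arm's relative risk (end of treatment against baseline) carries two quantities: the share of baseline cases still ill, and the share of baseline non-cases newly ill. The SAP recognises that not everyone has both disorders, but handles this by changing the quantity estimated from remission to change in prevalence.

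Two consequences follow. With similar onset in both arms, a real difference in remission is diluted. That matters when the hypothesis predicts similarity and no equivalence margin is given, because a non-significant interaction becomes easier to obtain. With onset that differs by arm, the interaction can be significant although remission is identical, and a reader would take it for a remission effect.

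**Working it through.** **No plan figure to reproduce.** The Sample size calculations section powers the second-stage comparison of switch with combination (242 per arm, two-sided alpha 0.05, power 0.80). It gives no power for the first-stage interaction.

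**Formula.** Let p be baseline prevalence (equal in expectation in the two arms), r remission among baseline cases, and o onset among baseline non-cases. Two groups at two times with an interaction is a saturated model, so each arm's relative risk is

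RR = [p(1 − r) + (1 − p)o] / p = (1 − r) + o(1 − p)/p,

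and the interaction is the ratio of the two RRs. A GEE fitted to one simulated data set gave 1.0952, the same as the ratio of cell proportions. The term o(1 − p)/p vanishes only if o = 0 or p = 1.

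**Inputs.** From the documents: N = 2710; dropout of 40% over 33 months (Sample size calculations) or 20% (Retention). Per arm this gives 2710 × 0.6 / 2 = 813, 2710 × 0.8 / 2 = 1,084, and 2710 / 2 = 1,355 with no loss. Assumed, because the documents do not give them: p, o, and remission of 50% vs 57%. Ratios are the lower-remission arm over the higher.

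**Equal onset, p = 0.5**
- Baseline cases only: 0.50 / 0.43 = 1.163.
- SAP model, onset 10%: (0.50 + 0.10) / (0.43 + 0.10) = 0.60 / 0.53 = 1.132.
- SAP model, onset 20%: 0.70 / 0.63 = 1.111.

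**Standard errors, 813 per arm, p = 0.5, onset 10%**
- Baseline cases (406.5 per arm): variance of the log ratio = (0.50/0.50 + 0.57/0.43) / 406.5 = 2.3256 / 406.5, so SE = 0.0756.
- SAP model: each arm contributes [1/P1 + 1/p − 2·p(1 − r)/(p·P1)] / n, where P1 is the end-of-treatment prevalence (0.300 and 0.265). This gives (2.000 + 2.528) / 813, so SE = 0.0746. With 20% onset it is 0.0739.

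The SE is slightly smaller under the SAP model. The power loss comes from the diluted ratio alone.

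**Power, two-sided 5%, onset 10% in both arms, complete data**

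| Baseline prevalence | Per arm | Baseline cases | SAP interaction |
|---|---|---|---|
| 0.5 | 813 | 51% | 38% |
| 0.5 | 1,084 | 63% | 48% |
| 0.5 | 1,355 | 73% | 57% |
| 0.74 (2000/2710) | 813 | 68% | 62% |
| 0.9 | 813 | 76% | 74% |

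Example, first row: ln(1.163)/0.0756 = 1.99 and ln(1.132)/0.0746 = 1.66, each compared with 1.96. At p = 0.9 and 20% onset the SAP figure is 73%, a loss of about 4 points.

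**Unequal onset, p = 0.5**
- Remission 50% vs 57%, onset 5% in the better arm and 10% in the other: 0.60 / 0.48 = 1.25, further from 1 than 1.163.
- Onset the other way round: 0.55 / 0.53 = 1.04.
- Remission 50% in both arms, onset 5% vs 15%: 0.65 / 0.55 = 1.18. In 2,000 simulated trials of 2710 participants the SAP interaction rejected in 87.0%, and the baseline-case analysis in 4.3%. At p = 0.9 the figures were 7.8% and 4.8%.

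With equal remission and equal onset, the SAP test kept its size (4.2% to 5.1%).

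**The case against.** The best defence is that the SAP model is a valid randomised comparison. It keeps everyone who was randomised, allows for chance imbalance in baseline prevalence, holds its size when neither remission nor onset differs, and is open about its reason. Change in prevalence is also of public-health interest. All of that stands; the difficulty is that it is not the quantity in Hypothesis 1a.

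A second defence is that Hypothesis 1a does not say per-disorder remission among baseline cases. The definition under Study visits can be read as requiring both disorders to be absent, in which case new PTSD in someone who entered with MDD counts against remission. This reading is open, so the SAP should settle it. It does not rescue the present model: under such a composite everyone is a case at entry, p is 1, and the SAP's reason for modelling change falls away.

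Third, restricting to baseline cases might seem to breach intention to treat. It does not, because disorder status is measured before randomisation and those participants are still analysed as randomised.

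A reader might also infer more than the documents support:
- That the non-cases never had the disorder. The SAP speaks only of baseline status.
- That including them adds variance. In the settings worked here it does not.
- That the bias always favours a finding of similarity. This requires similar onset in both arms, and also that a non-significant test be read as similarity, which the SAP does not say.
- That MDD is affected as much as PTSD. The Abstract's Methodology describes 2000 of 2710 participants as having MDD, about 74% before counting any among the other 710.

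**Conclusion.** The point holds as a mismatch between estimand and hypothesis. The primary interaction measures change in prevalence, and it answers the remission question only if new onset is negligible or the disorder is nearly universal at entry. With half having PTSD at baseline and 10% onset in both arms, about 13 to 16 points of power are lost across the three sample sizes. At 90% prevalence the loss is about 2 to 4 points with 10% to 20% onset. With unequal onset the direction cannot be predicted, and the test can reject when remission is equal.

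This rests on reading the two unnamed binary outcomes as MDD and PTSD, which the SAP's wording and its last paragraph suggest but do not state, and on assumed values for prevalence, onset and remission. The 813-per-arm figures apply 33-month dropout to an endpoint at month 3 or 6, so those power levels are probably too low; the drop persists at the larger sizes. The practical concern is mainly PTSD. The SAP should be changed, but its present comparison is not invalid.

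**What to change.** Name the two binary primary outcomes in the SAP. For each disorder, make the primary analysis of Hypothesis 1a remission at end of first-line treatment among participants who had that disorder at baseline, analysed as randomised. Adjust for baseline BDI-2 or PCL-5, as the protocol already plans, and for the stratifiers sex and delivery mode (telephone or in person). Report new onset among baseline non-cases by arm in a separate table. Keep the present time-by-group model as a supporting analysis, described as change in prevalence.

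The cost is SAP wording, one extra table and a smaller denominator per disorder, chiefly for PTSD. In the settings worked above with a real remission difference and equal onset, the smaller denominator still gave more power than the present model, because the ratio is no longer diluted. With zero onset the two analyses give the same ratio.

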Leveraging the Depression And Primary-care Partnership for Effectiveness-implementation Research (DAPPER) – will be initially randomized to 12 weekly one-hour sessions of IPT (3 months) or 6 months of fluoxetine (tapering up to 60mg). Those participants who are not in remission with at the conclusion of initial treatment will be re-randomized to second-line treatment (see below). Prior to randomization, participants will be given the option to receive their treatment at the health facility or by telephone.

Participants who are randomized to fluoxetine and conduct their visits by telephone will need to collect their medication at the health facility. If participants do not collect their medication at the health facility, fluoxetine may be delivered to participants in the community. A smaller, Part 2, of the study will consist of qualitative interviews and focus groups to assess the overall implementation strategy and gather feedback on the specific interventions. Please see "Part 2," below (and additional consent for this aspect of the study, attached).

Randomization and blinding: Randomization will take place after baseline measures are complete. Randomization will be done in blocks of 10 and stratified by sex and telephone vs in-person treatment to ensure that the treatment groups are approximately equal in size and in gender distribution and telephone vs in-person treatment. See below

for second randomization information. Clinical evaluators who conduct follow-up assessments will be blinded to treatment assignment. Participants, IPT therapists, fluoxetine providers cannot be blinded because they will either be providing or receiving the IPT and/or Fluoxetine treatment and therefore they will know their treatment status. In addition, at least one study coordinator will not be blinded to assist with tracking of participants.

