used in 2 ongoing studies in Kisumu, Kenya.(Onu et al., n.d.) These are a mixed method study whose main objective is to identify the mental health impact of providing testimony to FIDA legal providers for women with claims related GBV and a capacity Building Randomized Controlled Trial of Interpersonal Psychotherapy for HIV+ Women Affected by Gender Based Violence. The studies are not formal psychometric evaluation/validation studies, but show acceptability and convergent validity. As the results of those measures were corroborated by qualitative assessments. The BDI also showed convergent validity in Luo (as well as the Kiswahili) with the MINI MDD diagnosis.

Table 1: SMART-DAPPER Measures	
Variable	Description
Demographics	Age, gender, marital status
Highest education	(1) None; (2) primary; (3) secondary; (4) tertiary and beyond
Individual income and employment, education, assets, school fees, and time allocation	Assessment of individual formal and informal income and employment, assets, education, and time allocation
Health co-morbidities	HIV, Malaria, HTN, DM
Proximity to clinic*	Location of residence relative to KCH and other Kisumu County Ministry of Health facilities
Overall challenges for attending depression care appointments at KCH and other Kisumu County Ministry of Health facilities, and by telephone and identification of top challenge*	(1) easy challenge (2) moderate challenge (3) difficult challenge (4) impossible or nearly impossible challenge; (5) Identify source of the greatest challenge in text (e.g., money, logistics, stigma, etc.)
Cost of transport from residence to KCH and other Kisumu County Ministry of Health facilities, and any associated telephone costs **	(1) 0-100KSH (2) 100-300KSH (3) 300-500KSH (4) more than 500KSH

Opportunity costs per depression treatment session: lost wages, dependent care**	(1) 0-100KSH (2) 100-300KSH (3) 300-500KSH (4) more than 500KSH
Major Depressive Disorder (MDD)	Beck Depression Scale (BDI)(Beck, Ward, Mendelson, Mock, & Erbaugh, 1961), MINI MDD module (D V Sheehan, 1998)
Post-traumatic Stress Disorder (PTSD)	Posttraumatic Stress Checklist (PCL-5), MINI PTSD module (D V Sheehan, 1998), Primary Care PTSD Screen for DSM-5 (PC-PTSD-5) (Prins A, 2015)

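### The SAP's first-line models omit both stratification factors and the protocol's covariates without a reason; if those factors predict change, reported standard errors are slightly conservative

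*SAP*

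**What the plan says.** **Allocation.** Under Randomization and blinding, the protocol says: "Randomization will be done in blocks of 10 and stratified by sex and telephone vs in-person treatment". Participants choose their delivery mode before they are randomised, so both factors are baseline variables.

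**SAP, binary primary outcomes.** The model is a GEE "log-link binomial regression model with robust standard errors and a working exchangeable correlation structure". On its terms the SAP says "our model included the predictors of time (e.g., baseline and end of treatment), intervention group, the interaction of time, and intervention group".

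**SAP, continuous secondary outcomes.** The model is a linear GEE, and "our model included the predictors of time (baseline, end of treatment), intervention group and the interaction of time and intervention group". For both sets of outcomes, "The primary test of interest is the time by group interaction".

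**Protocol, Data analysis plan, Hypothesis 1a.** This is a logistic model for remission with treatment group plus "demographics and severity of baseline depression and/or PTSD symptoms (BDI and PCL"). Table 1 defines the demographics entry as "Age, gender, marital status", so sex is arguably covered there. Delivery mode is not named.

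**Second stage.** The re-randomised comparisons use Fisher's "exact test for MDD or PTSD or an exact Wilcoxon rank-sum test for BDI-2 score or PCL-5 score". The documents do not say whether the re-randomisation was stratified, so this point is confined to the first-line models.

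**The concern.** Stratified blocks keep the arms balanced on sex and delivery mode. Outcome variation due to those factors therefore largely drops out of the true sampling error of the treatment comparison. A model that leaves the factors out still counts that variation as noise when it estimates the standard error. Intervals then come out wider than the design warrants, and tests fall a little below their nominal size.

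The SAP is also thinner than the protocol. Sex (through demographics) and baseline severity are in the protocol's Hypothesis 1a model and absent from the SAP's, with no reason given. Delivery mode is in neither.

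The stakes are modest but not nil. Hypothesis 1a predicts similar efficacy, the SAP's test is a test of difference, and neither analysis section states an equivalence margin. A slightly conservative test makes a non-significant result slightly more likely, and such a result could be read as support for the hypothesis.

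**Working it through.** **Plan's own figures.** Neither document gives a standard error, a precision target or a prognostic strength for the first-line models, so there is no stated figure to reproduce. The sample size does not depend on this point. It rests on second-stage comparisons (242 per arm; 4 × 242 = 968; 968 / 0.5 = 1936; 1936 × 1.4 = 2710.4, stated as 2710).

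**Step 1: the tested parameter.** With two time points and complete data, the time-by-group term in the linear model is the difference between arms in mean change. A factor that shifts baseline and end of treatment equally cancels from it. What matters is R², the share of the variance of *change* explained by sex and mode together.

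**Step 2: size of the excess.** With balance within strata, true SE / reported SE = k = √(1 − R²), so the excess is 1/k − 1. The actual size of a nominal two-sided 5% test is 2 × [1 − Φ(1.96 / k)]. If the reported SE implies 80% power, the corrected SE implies Φ[(1.96 + 0.8416) / k − 1.96]. R² is assumed throughout.

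| R² | k | SE excess | Actual size | 80% becomes |
|---|---|---|---|---|
| 0 | 1.0000 | 0 | 5.0% | 80.0% |
| 1% | 0.9950 | 0.5% | 4.9% | 80.4% |
| 2% | 0.9899 | 1.0% | 4.8% | 80.8% |
| 5% | 0.9747 | 2.6% | 4.4% | 82.0% |
| 10% | 0.9487 | 5.4% | 3.9% | 84.0% |

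**Step 3: simulation, linear model.** The settings were 2,000 participants, blocks of 10 within sex by mode, assumed shares of 60% and 40% for the two factors, robust errors and 2,500 replicates. At R² = 5% the empirical SD of the estimate was 0.0429 with or without adjustment. The mean reported SE was 0.0447 unadjusted and 0.0436 adjusted, a ratio of 0.974 that agrees with Step 2. The estimate was already as precise as the design allows, and only its reported error was too large.

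**Step 4: which terms are needed, linear model.** Adding sex and mode as main effects only, with 800 participants, left the interaction estimate unchanged (difference below 1e-15) and the mean SE at 0.0700 in both fits. The reduction appears only when the factor-by-time terms are added.

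**Step 5: the SAP's log-link binomial GEE.** The settings were 2,000 participants and 1,000 replicates, with assumed average risks of 0.75 at baseline and 0.45 at end of treatment. Each factor had an assumed baseline risk ratio of 1.05, and outcomes were independent over time given stratum.

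| Risk ratio per factor at end | SE cut, main effects only | SE cut, with time terms | Fall in empirical SD, with time terms |
|---|---|---|---|
| 1.05 | 0.2% | 0.3% | 0.2% |
| 1.2 | 0.4% | 1.0% | 0.7% |
| 1.4 | 0.8% | 3.4% | 1.8% |

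Missing data and multiple imputation were not modelled.

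**The case against.** **The consequence is conditional.** The excess exists only if sex or mode predicts change from baseline, and the documents give no figure for either. The one hypothesis about delivery mode (6a) concerns retention, not remission. This stands, and it is why the size is given as a range that includes zero. The documents do make some prognostic value plausible. Mode is self-chosen, telephone delivery came in with the pandemic, and Hypothesis 3a expects transport time or cost to modify the treatment effect.

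**A reader might infer that precision has been thrown away.** For the estimate itself this is largely wrong. Stratified allocation already delivers the precision. In the linear model adjustment does not change the estimate's variability, and in the log-link model it reduces it by at most 1.8% in the settings tried.

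**A reader might also infer a large gain.** Simulations of 800 per arm, with about 50% remission, give a variance 8% smaller after adjustment if each factor shifts remission by 20 points, and 17% smaller at 30 points. The documents support neither shift, nor the assumed 70/30 sex and 50/50 mode splits. Interval width follows the standard error, so the variance ratios of 0.924 and 0.830 mean intervals about 4% (√0.924 = 0.961) and 9% (√0.830 = 0.911) narrower. At 10 points the variance gain is about 2%, or about 1% in width.

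**Little hangs on it.** The sample size was set for second-stage arms of 242, while the first-line contrasts use the whole randomised sample. No conclusion has been shown to turn on an SE change of this order. That also stands. It limits the priority of the point, but it does not explain why the SAP leaves out the factors the trial was stratified on.

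**Conclusion.** The omission is a matter of record: sex and delivery mode define the strata and appear in neither first-line SAP model. The protocol's adjustment for demographics and baseline severity has also been dropped without a reason. The consequence depends on assumed prognostic strength. Reported standard errors for the time-by-group test are about 0.5% to 5% too large if the factors explain 1% to 10% of the variance in change, and correct if they explain none. In the log-link settings tried, the reported SE could be cut by 0.3% to 3.4%.

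The error is in the conservative direction. The documents do not support reading it as bias, an inflated false-positive rate or an invalid primary analysis. It is a small, inexpensive improvement that brings the analysis into line with the randomisation.

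**What to change.** 1. Add sex, delivery mode as chosen before randomisation, sex × time and mode × time to both first-line GEE models (log-binomial and linear). Do not settle for main effects alone.
2. Keep the marginal time-by-group contrast as the estimand: a ratio of relative risks for the binary outcomes and a difference of differences for the scores.
3. Name one fallback in advance if the log-binomial fit does not converge: a log-link Poisson working model with robust errors.
4. Put the same factors in the imputation model, so that it is no poorer than the analysis model.
5. State why the protocol's adjustment for demographics and baseline severity was dropped, or restore it.
6. State how delivery mode is coded for any participants enrolled before the telephone option existed.

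Both factors are known for everyone stratified on them, so no new data are needed. The SAP is written in the past tense, so the analysis may already have been run. In that case the cost is a small re-analysis, with the adjusted fit labelled as a sensitivity analysis beside the unadjusted one.
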